8.2. Partial dates

Missing months will be taken as June and missing days will be taken as the 15th day of the month.

8.3. Derived Variables

SASSAD scores will be computed prior to data entry. This will be checked using the individual components within the analysis files.

The proportion of time spent moving during the night will be obtained using accelerometers. The average of the first three nights of usable data at week 0 and the last three nights of usable data at week 12 will be used. Usable data is defined as values greater than 5% and less than 95% of the night spent moving to remove outliers. If there are less than three usable nights data, then this variable will be considered missing.

Patient Orientated Eczema Measure (POEM) scores will be calculated as a score between 0 and 28 based on seven symptoms. Parents are asked to state the number of days in the last week their child has been affected by each symptom. These are scored as follows; no days=0, 1-2 days=1, 3-4 days=2, 5-6 days=3 and everyday=4. The POEM score is the calculated as the sum of these 7 individual scores.

Totally Controlled Weeks (TCW) will be defined as zero days with an eczema bother score greater than 4 and zero days where "stepping up" of treatment was needed. Well-Controlled Weeks (WCW) will be defined as two days or less with an eczema bother score greater than 4 and two days or less days where "stepping up" of treatment was needed. The eczema score is recorded by the parent each day using a symptom diary and is based on how much bother the child's eczema has been that day. The score is on a scale from 0 to 10 where 0 equals no bother at all and 10 equals the most bother you can imagine. The definition of "stepping up" varies from child to child and is documented in the symptom diary for the parent to refer to after discussion with the nurse at the beginning of the trial.

Dermatitis Family Impact (DFI) scores will be calculated as a score between 0 and 30 based on ten questions. Parents are asked to state how much the child's skin problem has affected the family over the last week. These are scored as follows; not at all=0, a little=1, a lot=2 and very much=3. The DFI score is the calculated as the sum of these 10 individual scores.

Age (in years and months) will be calculated at randomisation.

Previous treatment history will be assessed using treatment reported at enrolment. This will be grouped into low strength (mild and moderate topical steroids) and high strength (potent and very potent steroids and mild and moderate calcineurin inhibitors). Participants will be classed as a low strength user if they only use mild and moderate topical steroids, and a high strength user if the use potent or very potent topical steroids or mild or moderate calcineurin inhibitors (even if they also use mild or moderate topical steroids).

8.4. Bias

The research nurses are blinded to treatment allocation throughout the study period. If any of the nurses feel that this blinding may have been compromised, details are logged centrally with the Trial Manager. A Sensitivity analysis will be conducted excluding those participants for whom the research nurse became unblinded to treatment allocation

during the trial. Integrity of information bias will be assessed using clinical photographs of a target lesion.

8.5. Data quality

Data queries will be resolved at data entry using a query form. To minimise errors, all primary outcome data will be verified by a data entry clerk who did not originally enter the data. A 10% sample of all other data will be checked for accuracy.

9. PARTICIPANT CHARACTERISTICS AND COMPLIANCE

9.1. Demographic and Baseline Characteristics

Demographic, disease severity, filaggrin status and other baseline characteristics will be cross-tabulated against randomised treatment allocation to check for appropriate balance. If substantial imbalance exists an additional adjusted analysis will be performed.

9.2. Compliance

Absence from the home will be used as the measure of compliance (recorded on the symptom diary).

A log of all protocol deviations will be kept by the Trial Manager which will be reviewed by the protocol violations committee at the end of the trial in order to assign the events as major or minor protocol deviations. Participants with major deviations will be excluded from the per protocol analysis.

9.3. Withdrawals

If participants choose to withdraw from the study, any units that have been installed will be removed as soon as is practicably possible. Participants will be asked to complete an end of study questionnaire at this time and diaries collected.

The number of participants who withdraw from the study with the reasons for withdrawal will be summarised by randomised treatment allocation.

10. EFFICACY

10.1. Primary Efficacy Analyses

The primary analysis will be the comparison of the change from baseline in SASSAD scores at 12 weeks between the two intervention groups using a t-test, including a p-value and confidence interval. This will also be expressed as the number needed to treat for a 20% reduction in SASSAD score at week 12 and a 50% reduction.

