8.3 Randomisation and blinding

Participants will be entered into a web-based randomisation programme by the Trial Manager, or Research Nurse. This will randomise them to one of the 2 treatment arms based on a computer generated code, using random permuted blocks of randomly varying size. This will be created by the Nottingham Clinical Trials Support Unit (CTSU) in accordance with their standard operating procedure, and held on a secure server. The randomisation will be stratified by age, disease severity (baseline SASSAD \leq 20, or SASSAD score \geq 20) and recruiting centre. Access to the sequence will be confined to the CTSU Data Manager. Allocation to treatment arms will be in the ratio 1:1 and the Trial Manager will access the treatment allocation for each participant by means of a remote,

internet-based randomisation system developed and maintained by the Nottingham CTSU. The allocation group will be indicated to the Trial Manager only after baseline data have been irrevocably entered into the randomisation programme. The sequence of treatment allocations will be concealed until interventions have all been assigned and recruitment and data collection are complete.

The research nurses will be blinded to treatment allocation throughout the study period and the trial statistician will analyse the results based on treatment code, using an analysis plan finalised prior to revealing the coded allocation sequence. Only after the analysis is complete will the actual treatment arms corresponding to treatment codes be revealed. The only study personnel in direct contact with study participants will be the research nurses and water engineers. The trial manager and study support staff at the co-ordinating centre in Nottingham will have telephone contact with parents of participants. Trial participants will continue to see healthcare professionals for their usual eczema care.

Since participants will not be blinded to the study intervention, an objective primary outcome has been chosen in order to minimise response bias, The primary outcome of disease severity, measured using the Six Area Six Signs Atopic Dermatitis scale (SASSAD) will be assessed by the research nurses who are blind to treatment allocation. This scale is based purely on physical examination of the skin and does not require input from the participants themselves. Other secondary objective outcomes include nocturnal movement (measured using accelerometers) and the use of topical therapy.

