10.3 Primary analyses

♦ Change in disease severity (SASSAD) at 12 weeks compared to baseline, will be assessed using Student's t-test. An adjusted analysis will also be conducted including the stratification variables of eczema severity, age and recruiting centre.

In order to aid the clinical interpretation of these data, the number needed to treat (NNT) assuming a range of improvements in SASSAD scores will also be presented ($\geq 20\%$, $\geq 50\%$ and $\geq 75\%$ improvement).

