5. ITT ANALYSIS AND MULTIPLICITY

The SWET trial will be analysed as intent-to-treat (ITT) at week 12.

The ITT population will consist of all randomised participants with evaluable data. This will be the primary population used for the main analysis, which will use the randomised treatment allocation rather than actual treatment received. An additional sensitivity analysis will be performed excluding outliers.

Primary inference will be based on the primary endpoint analysis of the ITT population. Significance will be at the 5% level.

A secondary, per protocol analysis of the primary endpoint will be performed excluding the following participants:

- Those who were randomised into the study, but who failed to receive their allocated treatment.
- Those who are deemed to be major protocol violators as determined by the Protocol Violators Group (including independent members) review of the protocol deviation log.

Criteria for protocol violators are as follows:

- Missing SASSAD score at week 12
- Group A: exposed to fully softened water for <75% of the time their home has an active water softener in place (i.e. sleeping at home + unit fully working for <75% of the time their home has an installation)

- Group A: Participant away from home or with partially functioning water softener of >2 days/week for each of the 4 weeks prior to the primary outcome measure
- Group B: Participant away from home for > 2 days/week for each of the 4 weeks prior to the primary outcome measure
- Unblinding of research nurse prior to primary outcome measurement
- Starting new treatment prior to primary outcome measurement will be examined on a case-by-case basis to determine if they comprise a protocol violator.

Baseline characteristics (as described in section 6.2) will be summarised and if any major imbalance exists the analyses will be adjusted to account for this.

Analyses of all secondary endpoints and adjusted analyses will be considered supportive to the primary analysis so no adjustments for multiple comparisons will be made.

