6. STRATA AND COVARIATES

6.1. Stratification variables

Randomisation is stratified by the following:

- Disease severity (baseline SASSAD ≥10 to ≤ 20, or SASSAD score >20)
- Recruiting centre

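### The primary t-test on change in SASSAD is valid and adequately powered, but it is not adjusted for baseline or the randomisation strata, and the SAP leaves the planned adjusted analysis unspecified

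*Combined protocol and SAP*

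**What the plan says.** SAP 10.1 makes the primary analysis a "comparison of the change from baseline in SASSAD scores at 12 weeks between the two intervention groups using a t-test", with a confidence interval and p-value and no covariates. Protocol 10.3 names the same test for the change in SASSAD ("will be assessed using Student's t-test") but adds, without condition: "An adjusted analysis will also be conducted including the stratification variables of eczema severity, age and recruiting centre". SAP 10.1 contains no such model.

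On the strata, protocol 8.3 says "The randomisation will be stratified by age, disease severity" and recruiting centre. SAP 6.1 lists only "Disease severity (baseline SASSAD ≥10 to ≤ 20, or SASSAD score >20" and recruiting centre; SAP 6.2 places age among the other covariates for the predictors-of-response model.

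On adjustment, the SAP has three statements:
- Section 5: "if any major imbalance exists the analyses will be adjusted to account for this".
- Section 5, a sentence later: "Analyses of all secondary endpoints and adjusted analyses will be considered supportive to the primary analysis".
- Section 9.1: "If substantial imbalance exists an additional adjusted analysis will be performed".

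Neither section defines a major or substantial imbalance, or names the covariates or model that would follow.

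**The concern.** Stratified allocation makes the arms alike on severity and centre, so the true sampling variance of the treatment difference falls when those factors predict change. A two-sample t-test still counts that between-stratum variation as noise. Its standard error is then larger than it need be, its type I error lies below 5%, and its interval is wider than the data require. Change from baseline usually depends on baseline through regression to the mean, and a minimum entry score of 10 (protocol 7.1) makes that more likely here.

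The second issue is pre-specification. The protocol commits to an adjusted analysis. The SAP, which governs the analysis, mentions adjustment of the treatment comparison mainly as a response to what the baseline table shows, and words that response in two ways. At stake are precision on the main result and certainty about which adjusted result will be reported.

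**Working it through.** **1. The plan's own figure.** Inputs from protocol 10.2 and SAP 4: difference 20% of 20 = 4 points, SD of change 10, significance level 5% (taken as two-sided), power 90%, attrition 15%.

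n per arm = 2 × (1.960 + 1.282)² × 10² / 4² = 131.3, so 132 per arm and 264 evaluable. Recruited: 264 / 0.85 = 310.6, so 311 against 310 stated. With 310 × 0.85 = 263.5 evaluable (131.75 per arm), the standard error is 10 × √(2/131.75) = 1.232, the 95% half-width is 1.96 × 1.232 = 2.41, and power is Φ(4/1.232 − 1.96) = 90.1%. The figure reproduces, and it was computed for this t-test.

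**2. Adjusting for baseline, equal SDs.** With baseline in the model, the treatment estimate is the same whether the outcome is the week-12 score or the change. Write ρ for the baseline to week-12 correlation, which the documents do not give. If the two SDs are equal, the ratio of ANCOVA to t-test variance is (1 − ρ²) / [2(1 − ρ)] = (1 + ρ)/2.

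| Assumed ρ | Variance ratio | Residual SD | Half-width | Power | Recruits for 90% power |
|---|---|---|---|---|---|
| t-test | 1 | 10 | 2.41 | 90.1% | 311 |
| 0.3 | 0.65 | 8.06 | 1.95 | 98.1% | 203 |
| 0.5 | 0.75 | 8.66 | 2.09 | 96.3% | 233 |
| 0.7 | 0.85 | 9.22 | 2.23 | 94.1% | 264 |
| 0.9 | 0.95 | 9.75 | 2.35 | 91.5% | 295 |

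**3. Adjusting for baseline, unequal SDs.** Hold the change SD at 10 and assume a baseline SD s. The week-12 SD w solves s² + w² − 2ρsw = 100, and the ratio is w²(1 − ρ²)/100. For s = 6 and ρ = 0.5: w² − 6w − 64 = 0, so w = 3 + √73 = 11.54, and the ratio is 133.3 × 0.75 / 100 = 1.00.

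| Assumed baseline SD | ρ = 0.3 | ρ = 0.5 | ρ = 0.7 |
|---|---|---|---|
| 6: ratio (power) | 0.91 (92.6%) | 1.00 (90.1%) | 0.89 (93.0%) |
| 8: ratio (power) | 0.72 (97.0%) | 0.94 (91.7%) | 0.97 (90.9%) |

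The gain vanishes exactly when change is uncorrelated with baseline, that is when ρw = s.

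**4. Behaviour under stratified allocation.** Simulation of 264 children, 4,000 runs per setting, blocks of 4 within 8 centres × baseline above or below 20, normal scores with equal SDs, no centre effect and age not simulated:

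| ρ | Type I error, t-test / ANCOVA | Power for 4 points, t-test / ANCOVA | Half-width, t-test / ANCOVA |
|---|---|---|---|
| 0.3 | 2.5% / 4.3% | 92.7% / 97.8% | 2.42 / 1.96 |
| 0.5 | 3.3% / 4.8% | 92.2% / 96.1% | 2.42 / 2.10 |
| 0.7 | 4.4% / 5.1% | 91.2% / 94.0% | 2.42 / 2.23 |

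The t-test interval covers 97.5%, 96.8% and 95.7% under no effect, so it errs on the safe side.

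**5. The text on adjustment.** Protocol 10.3 plans an adjusted analysis always. SAP 9.1 adds one only under substantial imbalance. SAP 5 adjusts the analyses themselves under major imbalance, yet also ranks adjusted analyses as supportive. These cannot all describe one plan.

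**The case against.** The strongest defence is that the trial was sized for exactly this test, using the SD of change, and that the calculation reproduces. That stands: a reader might infer that the trial is underpowered or its primary test unsound, and neither follows. The error is conservative, and what is lost is a possible gain.

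It can also be said that baseline is not ignored, because a change score subtracts it. That stands too; what is missing is regression on baseline.

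The size of the gain is open to challenge. Equal SDs with a change SD of 10 need a baseline SD of 8.5, 10.0 or 12.9 at ρ of 0.3, 0.5 or 0.7. With a floor of 10 and a mean of 20, an SD of 10 already implies a distribution as skewed as a shifted exponential. The larger gains therefore cannot be taken as expected.

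A reader might also infer that the primary estimate can be picked after the baseline table is seen, or that the SAP withdrew a primary adjusted analysis. The documents do not support either. SAP 5 bases primary inference on the primary endpoint analysis and calls adjusted results supportive, SAP 10.1 names the t-test, and protocol 8.3 requires the plan to be final before the coded allocation is revealed. The protocol's adjusted model was always an addition to the t-test. What remains is one loose clause in SAP 5, its mismatch with 9.1, and a planned model left unspecified.

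**Conclusion.** The point holds as one of forgone precision and incomplete specification. The planned test is valid, conservative whenever change is related to baseline or centre, and gives about 90% power under the plan's own assumptions. Adjusting for baseline would do anything from nothing (baseline SD 6, ρ = 0.5) to cutting the variance by about a third (equal SDs, ρ = 0.3), which would take power from 90% to about 98%. Both ρ and the baseline SD are assumptions, so no single figure should be quoted as the gain.

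The document faults need no assumption. The adjusted model of protocol 10.3 is absent from SAP 10.1, the two imbalance triggers differ and have no threshold, and age is a stratum in the protocol but not in the SAP. Which stratification list is correct cannot be settled from the documents: the randomisation may have changed, or one text may be wrong. The protocol's severity groups also appear to overlap at a score of 20 where the SAP's do not, though that may be a fault of text conversion.

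**What to change.** Before unblinding:

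1. In SAP 10.1, make the primary estimate the adjusted mean difference in week-12 SASSAD from a linear model with arm, continuous baseline SASSAD, centre and any other factor actually used in the randomisation, with 95% confidence interval and p-value.
2. Keep the t-test on change as a sensitivity analysis.
3. Delete the imbalance-triggered adjustment of the primary analysis from SAP 5 and 9.1.
4. Check the randomisation system and make protocol 8.3 and SAP 6.1 agree with it on age and on the SASSAD cut at 20. Include age in the model either way: as a stratum if it was one, otherwise as a pre-specified covariate, in keeping with protocol 10.3.

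The cost is SAP wording and one check of the randomisation specification. The covariates are already collected, and the sample size need not change.

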10.2. Secondary Efficacy Analyses

- 1) The difference between baseline and week 12 of the proportion of time spent moving during the night will be compared across intervention groups using a t-test. The average of the first three nights of evaluable data at week 0, and the last three nights at week 12 will be used.
- 2) The proportion of children who report a reasonable (≤20%), good (>20% and ≤50%) or excellent (>50%) improvement in SASSAD score at 12 weeks, will be compared using a chi-squared test.
- 3) Amount of topical corticosteroid / calcineurin inhibitors used during the 12 week study period. This will be captured by weighing the medication at each visit. This will then be summarised by the nurses at week 12, including a measure of the degree of accuracy of any estimates. These will be spilt into two groups, low strength consisting of mild and moderate topical steroids, and high strength consisting of potent and very potent topical steroids and mild and moderate calcineurin inhibitors. The difference in the amount (in grams) of each of the two groups will be assessed using t-tests.
- 4) The difference in the change from baseline to week 4 and baseline to week 12 Patient Oriented Eczema Measure (POEM) scores will be compared using t-tests.
- 5) Difference in the number of well controlled weeks (WCW) as defined in section 8.3, will be analysed using a t-test. The number of totally controlled weeks (which are a subset of the WCW), will also be summarised.
- 6) Difference in the mean change from baseline in the Dermatitis Family Impact (DFI) questionnaire at 12 weeks, will be analysed using a t-test.

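### The primary SASSAD analysis is an unadjusted t-test on change; a pre-specified model with baseline SASSAD and the stratification factors would cost nothing and could be more precise

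*Combined protocol and SAP*

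**What the plan says.** SAP 10.1 defines the primary analysis as a "comparison of the change from baseline in SASSAD scores at 12 weeks between the two intervention groups using a t-test", reported with a p-value and confidence interval. It names no covariates.

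Protocol 10.3 also puts Student's t-test first, but then commits without condition: "An adjusted analysis will also be conducted including the stratification variables of eczema severity, age and recruiting centre". SAP 10.1 contains no such analysis.

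The SAP deals with adjustment in three other sentences:

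- SAP 5, on status: "Analyses of all secondary endpoints and adjusted analyses will be considered supportive to the primary analysis".
- SAP 5, on baseline characteristics: "if any major imbalance exists the analyses will be adjusted to account for this".
- SAP 9.1, on the same subject: "If substantial imbalance exists an additional adjusted analysis will be performed".

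SAP 6.1 lists two stratification factors, baseline SASSAD (cut at 20) and recruiting centre. Protocol 8.3 lists these and age. Every child has a baseline SASSAD, because protocol 7.1 requires a score of at least 10 for entry.

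SAP 10.2 uses the same kind of test for change in POEM and for the family impact score: "Difference in the mean change from baseline in the Dermatitis Family Impact (DFI) questionnaire at 12 weeks, will be analysed using a t-test". SAP 10.3 does so for week-4 SASSAD.

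**The concern.** Two pieces of information that the design guarantees are not used as covariates in the deciding comparison: each child's baseline score and the randomisation strata.

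- **Baseline.** A change score subtracts baseline with a slope fixed at 1. If the true slope of week-12 score on baseline is below 1, change still depends on baseline, and that variation stays in the error term.
- **Strata.** Stratified randomisation balances severity and centre between arms, so the true sampling error of the difference falls if those factors predict change. The two-sample t-test still counts their variation in its standard error, which is then too large.

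Both effects widen the confidence interval on the one comparison that carries the inference.

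The SAP's provision for adjustment does not settle the matter. Neither a major nor a substantial imbalance is defined. SAP 5 says that the analyses themselves are adjusted, whereas SAP 9.1 says that a further analysis is added. Whether the primary result changes would thus be decided after the baseline tables by arm have been seen.

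**Working it through.** **1. The plan's own figure.** Inputs from SAP 4 and protocol 10.2: difference 20% of a mean baseline of 20 = 4 points; SD of change 10; power 90%; significance 5%; attrition 15%. Two-sided testing is assumed, because only the filaggrin calculation in SAP 7 states it.

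n per arm = 2 × (1.96 + 1.2816)² × 10² / 4² = 131.3, so 132 per arm and 264 in total. Then 264 / 0.85 = 311, against 310 stated.

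Power with 310 × 0.85 / 2 = 131.75 per arm: SE = 10 × √(2/131.75) = 1.232; 4 / 1.232 − 1.96 = 1.287; power 90.1% (89.9% with the noncentral t). CI half-width = 1.96 × 1.232 = 2.41 points. The sample size is reproduced and fits the t-test.

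**2. Adjusting for baseline, closed form.** Let r be the correlation (in absolute value) of change with baseline. The residual SD is 10 × √(1 − r²). If the SD is the same at both visits and ρ is the baseline to week-12 correlation, this equals 10 × √((1 + ρ)/2). The documents give neither r nor ρ, so the values below are assumptions.

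| Analysis | Residual SD | Power, 4 points | CI half-width | Children to recruit for 90% |
|---|---|---|---|---|
| t-test on change | 10.00 | 90.1% | 2.41 | 311 |
| Adjusted, ρ = 0.3 | 8.06 | 98.1% | 1.95 | 203 |
| Adjusted, ρ = 0.5 | 8.66 | 96.3% | 2.09 | 233 |
| Adjusted, ρ = 0.7 | 9.22 | 94.1% | 2.23 | 264 |
| Adjusted, ρ = 0.9 | 9.75 | 91.5% | 2.35 | 295 |

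With SD of change fixed at 10, equal SDs imply a SASSAD SD of 10 / √(2(1 − ρ)) = 8.5, 10.0, 12.9 and 22.4 in the four rows. The larger values fit poorly with a mean of 20 and a floor of 10 unless the scores are strongly skewed. Without the equal-SD assumption, power is 90.1% at r = 0, 91.2% at r = 0.2, 94.3% at r = 0.4 and 96.3% at r = 0.5.

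**3. Effect of the stratification, by simulation.** 4,000 trials per scenario with 264 children, permuted blocks within two severity bands × eight centres, and total SD of change 10. Assumed, not from the documents: skewed baseline with mean 20, SD 8 and floor 10; blocks of 2 and 4; centres of equal expected size; the values of r and of the between-centre SD. The adjusted model contains group, baseline SASSAD and centre.

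| r | Centre SD | t-test type I error | t-test CI coverage | Power, t-test | Power, adjusted |
|---|---|---|---|---|---|
| 0 | 0 | 5.1% | 94.9% | 90.2% | 90.1% |
| 0.3 | 0 | 4.7% | 95.3% | 90.1% | 91.9% |
| 0.5 | 0 | 3.8% | 96.2% | 91.0% | 95.7% |
| 0.3 | 2 | 4.1% | 95.9% | 90.5% | 92.8% |
| 0.5 | 3 | 2.9% | 97.2% | 93.2% | 97.8% |

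Monte Carlo error on type I error is about ±0.7 points, so 4.7% cannot be told from 5%. In the last row the t-test's average SE is 1.23 against a true sampling SD of 1.085, about 13% too large (1.23 / 1.085 = 1.13).

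**The case against.** The strongest reply is that nothing here fails the plan. The sample size was set on the SD of change scores, which is the quantity that the t-test uses. The test reaches about 90% power in every scenario examined, the estimate is unbiased, and any error is on the conservative side. Adjustment is ranked second, not absent: protocol 10.3 commits to it and SAP 5 gives it supportive status. All of this stands. The loss is precision forgone against a better model, not a shortfall against the plan.

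It does not remove the reason to act. Covariance(change, baseline) = (slope − 1) × variance(baseline), so baseline is uninformative only if the week-12 slope is exactly 1, that is, with no regression to the mean. Even then the adjusted model costs essentially nothing (90.1% against 90.2%). And the SAP specifies no unconditional adjusted analysis of the primary endpoint to which its supportive status could apply.

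Three stronger readings are tempting, and the documents do not support them:

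- *The analysis ignores baseline SASSAD.* It does not. It subtracts baseline, with a fixed instead of an estimated slope.
- *The primary p-value and interval are known to be too conservative.* That depends on how far baseline and centre predict change, which the documents do not report.
- *The entry floor of 10 strengthens the case.* Under a linear relation, selection on baseline leaves the slope unchanged and shrinks the baseline variance, so baseline explains less. With an underlying mean of 16, SD 8 and slope 0.5, the correlation of change with baseline is −0.45 without the floor and −0.35 with it.

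**Conclusion.** The point holds as a free improvement, not as an error that invalidates the primary analysis. The unadjusted t-test is valid and meets its planned power. A pre-specified adjusted model would do at least about as well, and better to the extent that baseline SASSAD or centre predicts change.

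Under the closed-form assumptions the gain runs from nothing to about 8 power points (98.1% − 90.1%). The interval would be up to about 19% narrower (1.95 / 2.41 = 0.81). In the simulations the t-test's type I error ran from about 5% with no association to 2.9% at r = 0.5 and centre SD 3. These sizes rest on assumed correlations, baseline SD and centre variation, and only the direction is certain. For POEM and DFI the documents give no SDs, so the gain there is not quantified.

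Two inconsistencies hold whatever the correlation. The protocol's unconditional adjusted analysis is missing from SAP 10.1, and SAP 5 and 9.1 disagree on what an imbalance would trigger.

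**What to change.** 1. First reconcile protocol 8.3 and 10.3 with SAP 6.1 on whether age was a stratification factor.
2. In SAP 10.1, make the primary analysis a linear model of week-12 SASSAD on randomised group, with continuous baseline SASSAD and recruiting centre as covariates, plus age if it was a stratifier. Report the adjusted mean difference, its 95% CI and p-value. Keep the unadjusted t-test as a supportive analysis.
3. For the primary endpoint, replace the imbalance-triggered adjustment in SAP 5 and 9.1 with this fixed covariate set.
4. Amend the sentence in SAP 5 that ranks adjusted analyses as supportive, so that it no longer covers the primary model.
5. Use the same form for POEM, DFI and week-4 SASSAD, each with its own baseline.

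The cost is SAP wording before the allocation codes are revealed. It needs no new data and no change in sample size.
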